13.7 Publications and Clinical Study Report

13.7.2 Clinical Study Report

A clinical study report (CSR), written in accordance with the ICH E3 Guideline, will be submitted in accordance with local regulations.

During this COVID-19 pandemic, the safety of the subjects, investigators, and site personnel participating in these clinical studies is Vertex's first priority, thus it is important to minimize any unnecessary risk to COVID-19 exposure through travel to study sites. This addendum summarizes the measures taken for ongoing CF clinical studies. These operational adjustments were implemented to align with Health Authority guidance ensuring the protection of subjects, investigators, and site personnel while maintaining compliance with GCP and minimizing impact to the integrity of the studies. Overall, the benefit-risk of these studies remains favorable.

Vertex recommends that subjects and sites refer to local guidance regarding travel restrictions. There are no operational changes to the study protocols for subjects who can travel to the study sites for their visits. However, to ensure continued safety of subjects who *cannot* travel to the study sites for their visits (for any reason due to COVID-19), specific alternative measures are being implemented to minimize the risk of exposure to COVID-19 (see table below). As the COVID-19 pandemic evolves, Vertex will continue to assess the need for additional actions to ensure the safety of all involved in these clinical studies.

[figure not shown]
[figure not shown]
[figure not shown]
Addendum Version 2.0 summarizes additional measures taken for these ongoing CF clinical studies (see table below) to ensure continued safety. In addition, administrative changes were made to provide clarifications (e.g., changed Addendum 1 to Addendum Version 1.0) and to provide examples of qualified personnel (e.g., personnel from site or qualified health care agency) who may conduct safety assessments, as indicated per protocol, during in-home visits.

Summary of Changes in Ongoing CF Clinical Studies for Subjects Who Cannot Travel to the Study Site

Protocol Change	Rationale for Change	Study Number
Addendum Version 2.0, dated 15 May 2020		

Assessments
 
Weight and height/length/stature may be assessed by subjects or their caregivers using medical grade scales and stadiometers, as indicated per protocol and per local regulation. Sites and subjects will receive training and guidance as needed on these devices.
 
Subjects or caregivers will provide these measurements to site personnel by telephone or video call. Investigators will review results and contact subjects for follow-up as needed. All data will continue to be retained in the subject's source files.
	
To allow for collection of key data to assess safety and/or efficacy while maintaining study integrity and the safety of subjects and site personnel.
 
Addendum 1 allowed for these assessments to be performed by qualified personnel conducting the in-home visits. Addendum 2 allows for these assessments to be performed by subjects or caregivers.
	

 
VX18-561-101

Summary of Changes in Ongoing CF Clinical Studies for Subjects Who Cannot Travel to the Study Site

Protocol Change	Protocol Change	Protocol Change
Addendum Version 1.0, dated 24 April 2020		

Consenting of Subjects ICFs may be provided electronically or by post mail to subjects (and/or caregivers, as indicated per protocol). The subjects and/or caregivers will review the ICF with an appropriately qualified member of the investigator’s team via telephone contact or video call. After this review, subjects and/or caregivers will consent (or assent, if applicable), and/or re-consent verbally and by signing and dating the ICF and returning it to the site via post mail. The signed and dated ICF will then be signed and dated by the investigator.
 
Subjects participating in select studies may have the opportunity to enroll in longterm extension studies. Informed consent (or assent, if applicable), and/or re-consent for subjects (and/or caregivers, as indicated per protocol) may be obtained per the same process described above, as applicable.
	
To provide alternative methods of obtaining re-consent or consent, as applicable, while ensuring subject safety.
	

Study Drug Shipping Study drug may be shipped directly from the site to the subject, as applicable, and if permitted by local regulations; subject protected health information will not be released to Vertex.
 
Reconciliation, return, and destruction of study drug will continue to occur at the clinical site as indicated per protocol and in adherence to local regulations.
	
To ensure subjects can continue treatment with study drug without interruption while ensuring their safety.
 
To clarify that despite these alternative measures, reconciliation, return, and destruction of study drug will remain as indicated per protocol.
	

In-home Visits and/or Telephone Contact Study visits may be conducted as in-home visits by qualified personnel as requested by participating sites on a per-subject basis. In addition, all subjects may be contacted by site personnel by telephone or video call, irrespective of in-home visits.
	
To provide subjects the opportunity to continue participation in the clinical studies while ensuring their safety by minimizing the risk to COVID-19 exposure through travel.
	
VX18-561-101
 

Summary of Changes in Ongoing CF Clinical Studies for Subjects Who Cannot Travel to the Study Site

Protocol Change	Protocol Change	Protocol Change
Addendum Version 1.0, dated 24 April 2020		

Safety Assessments and Reporting
 
Safety assessments, as indicated per protocol, may be performed by qualified personnel conducting the in-home visits (e.g., personnel from site or qualified health care agency). These assessments may include the following, as indicated per protocol, and per local regulation:
 
 • vital signs • pulse oximetry • height/length/stature • weight • physical examination (complete or abbreviated) • pregnancy test (serum or urine) • urinalysis • blood draws for safety test panels (chemistry, LFT panel, lipid panel, hematology, coagulation). 
Blood and/or urine samples for safety assessments are analyzed as indicated per protocol for subjects who have in-home visits.
 
Blood and/or urine samples for safety assessments may be collected and analyzed at local laboratories for subjects who do not have in-home visits, but do not complete the assessment at the site.
 
In addition, safety assessments will be evaluated by telephone. These assessments may include the review of the following:
 
 • AEs • signs and symptoms/systems for CF • medications • planned or unplanned hospitalizations for CF • study drug administration • outcomes related to PEX • outcomes related to antibiotic treatment 
Investigators will review results (in-home and telephone) and contact subjects for follow-up as needed.
 
All data will continue to be retained in the subject’s source files.
 
Any clinically significant finding (e.g., AE, SAE, laboratory abnormalities) will continue to be reported as indicated per protocol.
	
To assess the safety and tolerability of the CFTR modulator evaluated in the specific clinical study while ensuring subject safety. These safety assessments will continue to provide safety data while minimizing burden to subjects and site personnel.
 
To clarify that despite these alternative measures, all adverse events and serious adverse events should be reported as indicated per protocol.
	

 
VX18-561-101
 

Summary of Changes in Ongoing CF Clinical Studies for Subjects Who Cannot Travel to the Study Site

Protocol Change	Protocol Change	Protocol Change
Addendum Version 1.0, dated 24 April 2020		

Efficacy and Other Assessments Efficacy and other assessments, as indicated per protocol, may be performed by qualified personnel conducting the in-home visits. These assessments may include the following, as indicated per protocol, and per local regulation.
 
In-home Spirometry Assessment A spirometry device may be provided to subjects for in-home assessments of lung function as indicated per protocol. Sites and subjects will receive training and guidance as needed.
 
Patient Reported Outcome CFQ-R questionnaires may be provided to subjects (electronically or post mail) to be completed at home as indicated per protocol. Subjects will return these questionnaires to the site via post mail.
 
Other Assessments
 
 • ECGs • sweat chloride • blood samples for CFTR genotype testing, [REDACTED], PK, FSH, [REDACTED], [REDACTED] 	
To be able to assess safety, treatment effectiveness, and quality of life measures of the CFTR modulator evaluated in the specific clinical study while ensuring subject safety.
	
All Efficacy and Other Assessments
 
[REDACTED]
 
VX18-561-101
 
Note: CFQ-R does not apply for [REDACTED] VX18-561-101
 
Other Outcomes Only
 
[REDACTED]
 
VX18-561-101

Summary of Changes in Ongoing CF Clinical Studies for Subjects Who Cannot Travel to the Study Site

Protocol Change	Protocol Change	Protocol Change
Addendum Version 1.0, dated 24 April 2020		

Remote Monitoring Vertex has implemented remote monitoring visits where applicable, including remote source data verification, as allowed per local regulations. Remote monitoring will focus on collection of safety data, and data supporting primary and key secondary endpoints.
	
To allow for review of key data to inform on the safety of subjects receiving treatment.
 
To allow for review of other key data to inform on the objectives of the study while maintaining study integrity and the safety of subjects and site personnel.
	

 
VX18-561-101

AE: adverse event; CF: cystic fibrosis; CFQ-R: Cystic Fibrosis Questionnaire-Revised; ECG: electrocardiogram; [REDACTED]; FSH: follicle-stimulating hormone; GCP: Good Clinical Practice; ICF: informed consent form; [REDACTED]; LFT: liver function test; PEx: pulmonary exacerbation; PK: pharmacokinetic; SAE: serious adverse event; [REDACTED]; [REDACTED]

3 INTRODUCTION

This statistical analysis plan (SAP) for the final analysis is based on the approved clinical study protocol (CSP), Version 2.0, dated 03 Oct 2019, and most recent approved electronic case report form (eCRF), and approved eCRF completion guidelines.

This is a Phase 2, randomized, double-blind study to evaluate the efficacy and safety of VX-561 in subjects aged 18 years and older with cystic fibrosis.

The planned statistical analyses will contribute to evaluation of VX-561 doses based on totality of data, along with PK analysis and PK/PD analysis.

Per Protocol Version 2.0, the VX-561 25 mg qd and 50 mg qd treatment arms were discontinued ([REDACTED]). Most of the subjects randomized to the two dropped dose arms did not complete treatment. Therefore, the statistical analysis should be interpreted with caution.

This SAP (Methods) documents the planned statistical analyses of efficacy and safety endpoints for the final analysis.

The pharmacokinetic (PK) and pharmacodynamic (PD) characteristics of VX-561 will also be evaluated in the study. Selected analyses related to sweat chloride will be documented in this SAP, other PK and PD analyses will be documented separately in the clinical pharmacology analysis plan (CPAP) and the Modeling and Simulation Plan for the study.

This SAP (Methods) will be finalized and approved prior to data lock and treatment unblinding for the final analysis.

The Vertex Biometrics Department will perform the statistical analysis within the scope of the SAP. SAS® Version 9.4 or higher software (SAS Institute, Cary, North Carolina, USA) will be used to generate all statistical outputs (tables, figures, listings, and datasets).

4 STUDY OBJECTIVES

4.1 Primary Objective

- To evaluate the efficacy of VX-561

4.2 Secondary Objectives

- To evaluate the PD effect of VX-561
- To evaluate the PK of VX-561, IVA, and relevant metabolites
- To evaluate the safety and tolerability of VX-561

5 STUDY ENDPOINTS

5.1 Primary Endpoint

- Absolute change in percent predicted forced expiratory volume in 1 second (ppFEV₁) from baseline at Week 12

5.2 Secondary Endpoints

- Absolute change in sweat chloride concentrations from baseline at Week 12
- PK parameters of VX-561, IVA, and relevant metabolites
- Safety and tolerability, based on the assessment of adverse events (AEs), laboratory test results, standard 12-lead ECGs, vital signs, and pulse oximetry

6 STUDY DESIGN

6.1 Overall Design

This is a Phase 2 study of VX-561 monotherapy. A schematic of the study design is shown in Figure 6-1, which is randomized, double-blind, parallel-group, and active-controlled. The study was planned to evaluate 4 dose levels of VX-561 in subjects with CF who have a gating mutation and were previously taking a stable dose of IVA. Randomization will be stratified by ppFEV1 value at Screening (<70 versus ≥70). Per Protocol Version 2.0, the VX-561 25 mg qd and 50 mg qd treatment arms were discontinued ([REDACTED]); 44 subjects had been enrolled and randomized to the 5 treatment arms at that point. The remaining subjects planned to enroll will be randomized 2:2:1 to 3 treatment arms (VX-561 250 mg qd, VX-561 150 mg qd, and IVA 150 mg q12h).

Figure 6-1 VX18-561-101 Study Design

Screening 28 days	Treatment Period 12 weeks	Washout Period 3-5 days	Safety Follow-up 28 days after last dose
Enroll Subjects on Stable IVA Treatment	VX-561 250 mg qd	Washout VX-561 or IVA	Resume IVA
	VX-561 150 mg qd		
	VX-561 50 mg qd (treatment arm discontinued)		
	VX-561 25 mg qd (treatment arm discontinued)		
	IVA 150 mg q12h		

6.2 Sample Size and Power

The primary objective is to evaluate efficacy of VX-561. The primary efficacy endpoint is the absolute change in ppFEV1 from baseline at Week 12. Following discontinuation of the VX-561 25 mg qd and VX-561 50 mg qd treatment arms, the remaining subjects planned for enrollment will be randomized in a 2:2:1 ratio to the 3 current treatment arms. Assuming a within-group SD of 7 percentage points and a 10% dropout rate at Week 12: a sample size of 22 to 28 subjects in the VX-561 150, and 250 mg qd arms will provide a 95% CI of ± 3.4 to ± 2.9 percentage points around the observed mean absolute change in ppFEV1 from baseline at Week 12, based on 2 sided, 1-sample t statistics; a sample size of 11 to 14 subjects in the IVA 150 mg q12h arm will provide a 95% CI of ± 5.4 to ± 4.4 percentage points around the observed mean.

6.3 Randomization

An interactive web response system (IWRS) will be used to assign subjects to treatment. A randomization list will be produced by Vertex Biostatistics or a qualified randomization vendor.

Subjects will be assigned a unique subject number. Only subjects who have completed screening assessments and are eligible for participation in the study will be randomized to receive study drug during the Treatment Period. Randomization will be stratified by ppFEV1 (<70 versus ≥70) determined during screening.

6.4 Blinding and Unblinding

Please refer to Section 10.7 of the CSP for details.

7 ANALYSIS SETS

The following analysis sets are defined: All Subjects Set, Full Analysis Set and Safety Set.

7.1 All Subjects Set

The **All Subjects Set** is defined as all subjects who were randomized or received at least 1 dose of study drug. The All Subjects Set will be used for individual subject data listings and disposition summary tables, unless otherwise specified.

7.2 Full Analysis Set

The **Full Analysis Set** (FAS) will include all randomized subjects who carry the intended *CFTR* genotype and have received at least 1 dose of study drug in the Treatment Period. The FAS will be used for all PD and efficacy analyses in which subjects will be analyzed according to their randomized treatment group, unless otherwise specified.

7.3 Safety Set

The **Safety Set** will include all subjects who received at least 1 dose of study drug. The Safety Set will be used for all safety analyses and study drug exposure, unless otherwise specified. Subjects will be analyzed according to the treatment they received.

If a subject received doses from multiple treatment groups, the subject will be analyzed in the group with the highest priority, according to the order (from low priority to high priority) of IVA, VX-561 25 mg, VX-561 50 mg, VX-561 150 mg, VX-561 250 mg.

8 STATISTICAL ANALYSIS

8.1 General Considerations

The Schedule of Assessments is provided in Section 3 of the protocol. The precision standards for reporting safety and efficacy variables are provided in an internal Biometrics document that specifies the programming rules including the precision for derived variables.

All individual subject data for those randomized or dosed with any amount of study drug will be presented in data listings.

Continuous variables will be summarized using the following descriptive summary statistics: the number of subjects (n), mean, SD, median, minimum value (min), and maximum value (max).

Categorical variables will be summarized using counts and percentages. Percentages will be presented to 1 decimal place.

Treatment-emergent (TE) period will include the time period starting from the date of the first dose of study drug to 28 days after the date of the last study drug taken in the treatment period, or the completion date of study participation, whichever comes earlier. The TE Period will be used for safety analyses unless specified otherwise.

Baseline value, unless otherwise specified, will be defined as the most recent non-missing measurement (scheduled or unscheduled) collected before the first dose of study drug. For ECG, baseline will be defined as the most recent non-missing pretreatment measurement (or the average of triplicate measurements, if the most recent non-missing pretreatment measurement is obtained in triplicate), before the first dose of study drug.

Absolute change from baseline will be calculated as postbaseline value – baseline value.

Relative change from baseline will be calculated as (postbaseline value – baseline value)/baseline value.

Unscheduled visits: Unscheduled visit measurements will be included in analysis as follows:

- In scheduled visit windows per specified visit windowing rules
- In the derivation of baseline and last on-treatment measurements
- In the derivation of maximum and minimum values during TE period, and maximum and minimum change from baseline values for safety analyses
- In individual subject data listings as appropriate

Visit windowing rules: The analysis visit windows for protocol-defined visits are provided in [Appendix A](#).

Incomplete/missing data will not be imputed, unless specified otherwise.

Outliers: No formal statistical analyses will be performed to detect or remedy the presence of statistical outliers, unless specified otherwise.

Multiplicity: There will be no multiplicity adjustment for performing multiple hypothesis tests, unless specified otherwise.

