^o Blood samples will be collected for PK analysis of VX-561 and metabolites or IVA and metabolites. The sample collected at Screening will be collected without regard to time of IVA dosing. On Day 1, samples will be collected before dosing (0 hours) and at 4 hours after dosing (relative to the morning dose). At Day 15, Week 4, Week 8, and Week 12, a predose sample will be collected before the morning dose. In a subset of subjects (up to approximately 20 subjects), additional samples will be collected at the Week 4 visit at 1, 2, 4, and 6 hours after dosing (relative to the morning dose). At the Washout Visit, a single sample will be collected prior to resumption of IVA. A single sample will be collected at the Safety Follow-up Visit for analysis of IVA for those subjects who resume IVA therapy. Acceptable PK sampling windows are provided in Table 11-1. At the ETT Visit, a single blood sample for PK analysis will be collected.

^p Study drug will be administered orally twice daily (Section 9.6). The last dose of study drug will be the morning dose on the Week 12 Visit. Subjects may resume their prior IVA therapy after the Washout Visit.

^q All medications taken from 28 days before the Screening Period through the end of the study will be recorded (Section 9.5).

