9.1.2 Treatment Period

The Treatment Period will last approximately 12 weeks. Treatment Period assessments are listed in [Table 3-1](#). Dosing details are in Section 9.6.

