9.3 Rationale for Study Elements

9.3.1 Study Design

Subjects will continue their stable IVA treatment through screening, and then be randomized to study drug treatment groups on Day 1 (VX-561 or IVA). The efficacy and PD of VX-561 will be assessed after 12 weeks of randomized treatment. IVA (150 mg every 12 hours [q12h]) is included as a reference arm, but with unequal randomization to provide greater information on VX-561 dose-ranging. After the Treatment Period, a 3- to 5-day Washout Period where subjects will take no CFTR modulators is included to collect additional PK and PD data and enable a more thorough evaluation of VX-561 exposure-response relationships.

Following completion of the Washout Period, subjects will resume their prior therapy with commercial IVA.

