8.4.1 Adverse Events

AEs will be classified as pretreatment AEs, treatment-emergent adverse events (TEAEs), or post-treatment AEs, defined as follows:

Pretreatment AE: any AE that started before the first dose date of study drug.

TEAE: any AE that worsened (either in severity or seriousness) or that was newly developed on or after the first dose date of study drug through the end of the TE Period.

Post-treatment AE: any AE that worsened or that was newly developed beyond the TE Period.

For AEs with completely missing or partially missing start dates, if there is no clear evidence that the AEs started before or after study treatment, the AEs will be classified as TEAEs during the Treatment Period.

Details for imputing missing or partial start dates of adverse events are described in [Appendix D](#).

An overview of all TEAEs will be summarized in the following categories and presented by treatment groups and VX-561 total:

- Number of TEAEs (total number of TEAEs only)
- Subjects with any TEAEs
- Subjects with TEAEs by strongest relationship
- Subjects with TEAEs by maximum severity
- Subjects with TEAEs leading to treatment discontinuation (discontinuation of any study drug)
- Subjects with Grade 3/4 TEAEs
- Subjects with related TEAEs
- Subjects with TEAEs leading to treatment interruption (interruption of any study drug)
- Subjects with serious TEAEs
- Subjects with related serious TEAEs
- Subjects with TEAE leading to death

The following summary tables of TEAEs will be presented by treatment groups:

- All TEAEs
- TEAEs by strongest relationship

- TEAEs by maximum severity
- TEAEs leading to treatment discontinuation
- TEAEs leading to treatment interruption
- Related TEAEs
- Serious TEAEs
- Related serious TEAEs
- TEAEs leading to death
- Grade 3/4 TEAEs

Summaries will be presented by MedDRA System Organ Class (SOC) and Preferred Term (PT) using frequency counts and percentages (i.e., number and percentage of subjects with an event). When summarizing the number and percentages of subjects, subjects with multiple occurrences of the same adverse event or a continuing adverse event will be counted once, and only the maximum severity level will be presented in the severity summaries, and the strongest relationship level in the relationship summaries.

All AEs, including pre-treatment AEs, TEAEs, and post-treatment AEs, will be presented in an individual subject data listing based on the All Subjects Set.

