8.4.3 Electrocardiogram

For the treatment-emergent ECG measurements, a summary of observed values and change from baseline values will be provided at each scheduled visit by treatment groups, for the following ECG interval measurements (in msec): RR, PR, QT, and QT corrected for HR intervals (QTcF), QRS duration, and HR (beats per minute).

The number and percentage of subjects meeting at least 1 threshold analysis criterion during the TE period, will be summarized by treatment groups. The threshold analysis criteria are provided in [Appendix E](#).

In addition, a listing containing individual subject ECG values will be provided. This listing will include data from both scheduled and unscheduled visits.

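### For VX-561 completers, about a quarter of the treatment-emergent window falls after the last VX-561 dose, mostly on resumed IVA, and the TEAE and threshold tables do not split it

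*SAP*

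**What the plan says.** **The window.** SAP 8.1 defines it as follows: "Treatment-emergent (TE) period will include the time period starting from the date of the first dose of study drug to 28 days after" dosing ends. In full, the treatment-emergent (TE) period closes at "28 days after the date of the last study drug taken in the treatment period, or the completion date of study participation, whichever comes earlier". It is the default for safety: "The TE Period will be used for safety analyses unless specified otherwise". Protocol 12.3.1 has the same definition.

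**What uses it.** SAP 8.4.1 counts as a TEAE any event that worsened or was "newly developed on or after the first dose date of study drug through the end of the TE Period". For ECG, SAP 8.4.3 says: "The number and percentage of subjects meeting at least 1 threshold analysis criterion during the TE period, will be summarized by treatment groups". SAP 8.4.2 and 8.4.4 do the same for laboratory tests and vital signs. Subjects are placed by the study treatment they received (SAP 7.3) and tabulated in five groups (SAP 8.4). No table in the available text separates time on study drug from time after it.

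**What happens after the last dose.** Protocol 9.1.2: "The Treatment Period will last approximately 12 weeks". Footnote p to Protocol Table 3-1 puts the last dose on the morning of the Week 12 Visit. Protocol 9.3.1 describes 3 to 5 days without any CFTR modulator and adds: "Following completion of the Washout Period, subjects will resume their prior therapy with commercial IVA". Footnote p is permissive instead: "Subjects may resume their prior IVA therapy after the Washout Visit". The Safety Follow-up Visit is 28 ± 7 days after the last dose (Protocol 9.1.4).

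**The concern.** A post-dose tail in a TE definition is usually follow-up off treatment. Here most of it is planned exposure to the comparator. A new ALT rise or QTcF change on resumed IVA, or an event provoked by stopping modulators, would be tabulated under VX-561 150 mg or 250 mg. All arms have the same washout and, where IVA is resumed, the same drug afterwards, so the tail tends to pull the VX-561 arms towards IVA.

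This matters because safety and tolerability of VX-561 is a secondary objective, and the Protocol synopsis says the all-arm safety analyses support dose selection. For spirometry and sweat chloride, SAP Appendix A (note 6) keeps assessments after the last dose out of the analysis visits, apart from the Washout and Safety Follow-up visits. The safety counts have no comparable rule.

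**Working it through.** **1. Check the timeline against the plan's own figure.** Screening 28 days + treatment 84 days + follow-up 28 days after last dose = 140 days = 20 weeks. This matches the approximately 20 weeks in the synopsis and shows that the washout lies inside the 28 days.

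**2. Inputs.** Last dose on study day 85 (Week 12 target, SAP Appendix A), or day 80 to 90 with the ± 5-day window. Washout 4 ± 1 days. Tail 28 days, or as short as 21 if an early Safety Follow-up ends participation.

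**3. Share of the window after the last dose** = tail / (last-dose day + tail).
- Nominal: 28 / (85 + 28) = 28/113 = 24.8%.
- Lowest: 21 / (90 + 21) = 21/111 = 18.9%.
- Highest: 28 / (80 + 28) = 28/108 = 25.9%.

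**4. Share on commercial IVA, if resumed straight after the Washout Visit** = (tail − washout) / (last-dose day + tail).
- Nominal: 24/113 = 21.2%, with the modulator-free gap taking 4/113 = 3.5%.
- Lowest: (21 − 5)/111 = 14.4%.
- Highest: (28 − 3)/108 = 23.1%.

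**5. Scheduled post-baseline measurements for a completer (Protocol Table 3-1).** The follow-up measurement enters a threshold count only if taken by day 28. On days 29 to 35 it falls outside the TE period.
- ECG: Week 4 and Safety Follow-up, so 1 of 2 is after dosing.
- Coagulation: Week 12 and Safety Follow-up, so 1 of 2.
- Chemistry and hematology: four on drug and one at follow-up, so 1 of 5.
- Vital signs: four on drug, one at washout and one at follow-up, so 2 of 6.

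**6. Illustrative dilution.** The documents give no event rates, so the rate ratio (RR) is assumed. If the whole tail runs at the IVA rate, with no residual or delayed VX-561 effect, the tabulated ratio is (RR × 85 + 28)/113.
- RR 2.0: 198/113 = 1.75. Over the shares in step 3: 2.0 − 0.259 = 1.74 to 2.0 − 0.189 = 1.81.
- RR 3.0: 283/113 = 2.50.
- If the tail instead kept the VX-561 rate, RR 2.0 would stay 2.0.

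**7. In subjects.** With a constant hazard and TE incidence p, the share of first events arising after the last dose is [(1 − p)^(85/113) − (1 − p)]/p. For assumed p of 5%, 10% and 30% this gives 24.3%, 23.8% and 21.6%. In an arm of 28, that is about 0.3, 0.7 and 1.8 subjects.

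**The case against.** The 28-day tail is prespecified identically in protocol and SAP, matches the follow-up target and applies to every arm. It can catch delayed effects. Protocol 5.1 reports slower clearance and a longer half-life for VX-561 than for IVA, so some exposure may persist early in the tail; the documents give no figure for how long. Subjects had to be receiving and tolerating IVA at entry (Protocol 8.1), so a constant rate of new toxicity on resuming it is not established.

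Much is already visible. Appendix A shows Safety Follow-up as its own visit in the by-visit summaries, related TEAEs have their own tables, and all AEs are listed individually. Safety is descriptive only, and with about 14 subjects on IVA, one subject is 1/14 = 7 percentage points. Step 7 moves fewer than two subjects per VX-561 arm.

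All of this stands. It limits the size of the problem and supports keeping the 28-day tables. It does not supply a tabulated split: by-visit summaries contain no TEAEs, and listings leave the reader to rebuild the counts by hand.

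**Conclusion.** The point holds for completers in the VX-561 arms. Nominally about 25% of their TE window (19% to 26%) is after the last VX-561 dose: about 4 days without a modulator, then about 24 days on commercial IVA if it is resumed. TEAE tables and threshold counts credit all of it to the study arm. ECG is most exposed, with coagulation on the same count. The time shares follow from the documents; the loss in event rates does not, and the 1.75 rests on the assumptions in step 6.

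A reader might infer that a quarter of every completer's safety data is misattributed. The documents do not support that. IVA-arm completers return to the same drug, so only the washout gap differs for them. Resumption is not stated as certain throughout. The completion-date cap shortens the tail when follow-up is early. A share of days is also not a share of events. Nor do the documents support resting dose-level safety statements on an on-treatment window alone, since that would drop delayed effects from those statements. This is a cheap improvement to the presentation, not an error that invalidates an analysis.

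**What to change.** Keep the 28-day TE tables as planned. Add to SAP 8.4.1 to 8.4.4 a supplementary presentation of the TEAE overview, the SOC/PT table and the threshold counts, by onset or measurement date:

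1. First dose through last dose date.
2. After the last dose through the Washout Visit, or until IVA is resumed.
3. From then to the end of the TE period.

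Use the Washout Visit date as the boundary between (2) and (3) when the IVA restart date is missing or partial. Never let an imputed restart date precede the last dose: SAP Appendix B sets a missing day to the first of the month, which could do so. For a subject with neither date, such as some early discontinuers, (2) and (3) can be combined. Show the subjects and subject-days behind each column, because the periods differ in length. Read dose-level safety from both sets of tables.

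The cost is SAP wording and one extra table set with small counts. AE onset dates (Protocol 13.1.1.3) and medication dates (Protocol 9.5) are already collected. Delayed-onset events leave column (1) but stay visible in (2), (3) and the 28-day tables.

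Separately, Protocol 9.3.1 (*will* resume) and Table 3-1 footnote p (*may* resume) must be reconciled.
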